3.5 Rationale for the dosage, route, regimen

We will include grass pollen allergy patients with pre-seasonal short-term and pre-seasonal injection scheme with Polvac™ SCIT at the USZ Allergy Unit (Head: [name]). After the patients have received the full cycle of SCIT (six injections) as a part of standard care, they will be randomized into one of the two study groups for one additional injection, which is to be given 4-6 weeks after the last SCIT cycle injection. Depending on the group allocation, patients will receive allergen by SCIT (or by ILIT). *Figure 2* illustrates schematically the study design and *Figure 3* shows the flow chart for the study participants.

Polvac™ Doses:

- SCIT (n=15): 0.5 ml Polvac™ (max maintenance dose, 2000 U).
- ILIT (n=15): 0.1 ml Polvac™ (400 U).

The SCIT dose is chosen as this is the recommended and standardized treatment dose for patients receiving SCIT with Polvac™ for treatment of grass pollen allergy. The ILIT dose is 1/5th of the maintenance SCIT dose. This has been safely administered in four patients treated off-label with Polvac™ at the USZ allergy in 2023 ([name] and [name], personal communication). These four patients received three injections in a dose escalating manner and with four-week intervals. The doses were 1/15th, 1/10th and finally 1/5th of the maintenance SCIT dose. An ILIT dose of 1/15th of the maintenance SCIT dose was safely administered three times in 30 patients in the aforementioned ongoing study with Polvac™ ILIT (BASEC 2021-02301).

3.6 Explanation for choice of comparator (or placebo)

No comparator or placebo is used in the current project.

3.7 Risks / Benefits

Benefits

- The study should improve our understanding of the immune responses stimulation after SCIT and ILIT, and could lead to novel developments in AIT, and especially, ILIT.
- All study participants will get one additional AIT injection (SCIT or ILIT), which may contribute to and even further consolidate the success of their therapy.
- Results from previous studies suggest that an ILIT injection on top of a full SCIT cycle may further improve the therapeutic efficacy.

- The study participants receiving an ILIT injection would get to know a new route of AIT. In the future, they may use this as basis for discussion with their treating allergist regarding a possible change in the treatment regimen, as an alternative to SCIT. The benefits being reduced treatment times and lower allergen doses with potentially less AIT-associated side effects.

Risks

The SmPc for Polvac™ is the reference sheet for evaluation of AEs (see Appendix 002). The following known SCIT-associated are mentioned

- AE: itch or swelling and rubor at the injection site that resolves without treatment by next day (27%, 125 events in 462 injections of 154 patients)
- AE: allergic symptoms - urticaria, tightness of chest, drop in FEV1 >40% (2%, 11 of 462 injections) treated with an antihistamine or a short acting beta-2 agonist. Every clinic offering AIT is equipped to deal with this AE, and patients are required to stay in the clinic for 60 minutes for observation to deal with these incidents.
- Unexpected AE: some few patients reported fatigue within 6 hours
- Severe AE: systemic allergic symptoms that required hospitalization: drop in blood pressure, generalized urticaria or deterioration by 40% of peak flow or FEV1 (0.2%, 1 of 462 injections)
- Generation of autoimmune antibodies may be a potential long-term effect of AIT. This has not been reported in any of the AIT trials with Polvac™.
- One study reported one patient with hypothyroidism with auto-antibodies among 72 patients treated by ILIT (patients were not treated with Polvac™ but with a comparable alum-based product).
- In all AIT procedures (ILIT, SCIT or SLIT), there is a risk of anaphylactic reactions that typically happens within minutes of the injections. This is a SAE that will required hospitalization.
- The fine-needle aspiration (FNA) of the previously injected lymph node is a minimally invasive procedure and comparable to the ILIT procedure, hence, the potential AEs of ILIT injection and FNA are similar: infection and bleeding (hematoma). These problems are very rare, and antiseptic and ultrasound-guided procedures further minimizes the risk.

All SAE will be reported to the sponsor within 24 hours. SAEs will be followed up until one month after the end of the treatment period.

To minimize the risk of any allergic AEs, the patients will receive an emergency set ("Allergie Notfallset") for self-medication in case of side effects after the patient has left the study site. The emergency set consists of two tablets of Xyzal® 5 mg and two tablets of Spiricort® 50 mg (Appendix 003). Patients will be advised on when and how to use the emergency set. Furthermore after ILIT treatment the patients have to stay one hour at the allergy unit for observation.

3.8 Justification of choice of study population

We plan to include 30 participants with allergic rhinitis due to sensitization to grass pollen allergens. We chose to include patients already undergoing AIT and not sensitized-only patients as to reduce risk of allergic side effects and to enable the injection of a higher allergen dose. As compared to a low dose, a high allergen dose is expected to trigger stronger immune responses thereby facilitating assessment of such responses, the primary objective of the study.

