6. STUDY DESIGN

6.1 General study design and justification of design

This is a prospective, comparative, clinical open label pilot study. From patients with grass pollen allergy who undergo a pre-seasonal SCIT scheme with Polvac™ Grass+RyeSCIT at the USZ Allergy Unit, 30 patients will be recruited for the study that is illustrated in Figure 2.

Four to six weeks after end of SCIT treatment (at maximal maintenance dose), the patients will be randomized to one out of two treatment groups and receive one additional allergen injection. Fifteen patients will be allocated to receive another subcutaneous injection with 0.5 ml (2000 U) Polvac™

Grass+Rye. The other 15 patients will be allocated to receive an intralymphatic injection of 0.1 ml Polvac™ Grass+Rye with 400 U allergen. Both SCIT and ILIT injections are performed by ultrasound-guidance as to assure injection into the lymph node (ILIT) or 1 cm next to the lymph node (SCIT).

The FNA of lymph node tissue will be conducted at 2, 6 or 24 hours after allergen injection. At the same time, FNA of a contralateral lymph nodes will be performed as baseline. Venous blood will be sampled at all visits: at baseline as well as after 2, 6 or 24 hours, after 7 days and after 28 days of the allergen ILIT or SCIT. The FNA is performed by ultrasound-guidance.

[figure not shown]

Figure 2. Study design illustrated schematically the open-label clinical pilot study for assessment of immunological and inflammatory responses to a single ILIT or SCIT in patients receiving grass pollen immunotherapy with Polvac™ Grass+Rye.

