7.3 Assignment to study groups

The 30 patients will be randomized to the two different equally-sized treatment groups (ILIT 400 U and SCIT 2000 U), with each 15 patients per group.

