8.1.2 Control Intervention (standard/routine/comparator treatment)

No control intervention is used in this study.

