11. STATISTICAL METHODS

11.1 Hypothesis

This study is a pilot study which goal is to describe the effect of ILIT on the immune cell composition and immune cell function in lymph nodes and in blood. We will compare this with the effect SCIT on the same, but not to confirm a hypothesis of a certain difference.

We will use a wide screening with several methods to describe the immune responses.

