11.4 Planned Analyses

The investigators and the appointed statistician will be responsible for the statistical analysis of the collected data. The statistical software used will be Graph Pad Prism®, SPSS®, or open-source software “R”.

We will apply descriptive statistics to describe frequencies, proportions and numbers for the various analysis to be performed. The data will be described with an average (mean or median) and with variances (confidence intervals or standard deviations or standard errors) depending on the type of data.

Data will typically be illustrated with scatter plots or with box plots with 90 and 10% whiskers. For multiparametric analysis, the results from different tests will be transformed/normalized (e.g. z-score normalization) to generate heat maps, and for the hierarchical clustering of treatments and phenotypes, we will apply The R Project with Euclidean metrics.

For comparative testing of the different treatment groups (SCIT versus ILIT), ANOVA is applied for continuous parametric data that fulfil the criteria for ANOVA. Kruskal-Wallis analysis are applied for non-parametric ranked data.

For changes over time within patients, dependent (paired) t-test may be used. No sex/gender difference analysis is planned.

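### Within-arm blood changes at day 7 and day 28 cannot be separated from any continuing response to the preceding SCIT course; section 11.4 could rest route claims on a baseline-adjusted ILIT-SCIT contrast.

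*Combined protocol and SAP*

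**What the plan says.** All participants share one prior treatment. Section 3.5 places the study injection "After the patients have received the full cycle of SCIT (six injections) as a part of standard care" and sets its timing as one "which is to be given 4-6 weeks after the last SCIT cycle injection". Section 3.8 gives the reason for this population ("We chose to include patients already undergoing AIT") as lower risk of allergic side effects and the possibility of a higher dose. It does not discuss carry-over from the course. Section 8.6 deals with pollen exposure and bars other allergen injections up to day 28, but is also silent on carry-over.

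Section 7.3 has two arms, "with each 15 patients per group", both injected. Section 8.1.2 states: "No control intervention is used in this study". The synopsis has three groups of 10 instead, but no uninjected group there either.

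Under section 8.2.1.3, blood is taken once before the injection, then at 2, 6 or 24 hours, day 7 and day 28. For lymph nodes, section 6.1 adds a contralateral node aspirated at the same time as the treated one.

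On analysis, section 11.4 compares SCIT with ILIT by ANOVA or Kruskal-Wallis. It does not say whether these run on follow-up values or on changes, and it names no covariate. It adds: "For changes over time within patients, dependent (paired) t-test may be used". Section 11.1 gives the study's goal as to "describe the effect of ILIT on the immune cell composition and immune cell function" in lymph nodes and blood.

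**The concern.** A paired test asks whether the mean change since baseline is zero. It does not ask what caused the change. The blood baseline falls 4-6 weeks after the last course injection, and day 28 falls 8-10 weeks after it (4+4 to 6+4 weeks). The readouts in sections 9.2.1.1 to 9.2.1.3 include grass-specific IgE, IgG and IgG4 and allergen-restimulated T cells, which a SCIT course can itself be expected to alter. If any of these is still moving, a within-arm test picks up the movement. One pre-injection sample cannot estimate a trend, and no arm shows the course without a further injection.

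The stake is interpretation. Section 4.1 sets a quantitative theory (same mechanism, less allergen reaching the node) against a qualitative one. Drift common to both arms would look like a shared response and lean towards the quantitative theory, even if neither injection caused it. Section 3.1 intends the results to inform timing and dosing in larger studies.

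**Working it through.** The plan states no sample size calculation, power, alpha, effect size or SD, so there is no figure to reproduce. What follows is an illustration under stated assumptions.

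**Inputs from the protocol.** n=15 per arm (7.3); baseline 4-6 weeks after the course (3.5); one pre-injection blood sample (8.2.1.3); paired t-test allowed, and ANOVA or Kruskal-Wallis between arms (11.4).

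**Assumptions, not in the protocol.** Two-sided alpha 0.05; normally distributed changes; no effect of the study injection; a mean drift d, in SDs of the paired change, that is the same in both arms; a correlation rho between pre-injection and follow-up values of 0.5 or 0.7, with equal variances at the two times.

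**Step 1: within-arm paired t-test.** The statistic follows a noncentral t with n-1 degrees of freedom and noncentrality d × √n. For n=15 the critical value is 2.145 on 14 df.

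| Drift d (SD) | d × √15 | Significant, n=15 | Significant, n=10 (synopsis) |
|---|---|---|---|
| 0 | 0 | 5.0% | 5.0% |
| 0.25 | 0.968 | 14.7% | 10.9% |
| 0.5 | 1.936 | 43.8% | 29.3% |
| 0.75 | 2.905 | 77.1% | 56.2% |

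**Step 2: the randomised contrast.** The expected ILIT-minus-SCIT difference in change is d - d = 0. In a simulation with 15 per arm (50,000 runs per drift value), the between-arm test of change was significant in 4.7% to 5.1% of runs at every drift. Shared drift cancels whether or not baseline is adjusted for. Adjustment is a gain in precision.

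**Step 3: size of that gain.** Take the follow-up variance as 1. Per-patient variances, in large samples, are:

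- ANOVA of follow-up values: 1
- ANOVA of change: 2(1 - rho)
- ANCOVA: 1 - rho²

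Against follow-up values the ratio is 1 - rho²: 0.75 at rho 0.5 (a cut of 25%) and 0.51 at rho 0.7 (a cut of 49%). Against change the ratio is (1 - rho²)/(2(1 - rho)) = (1 + rho)/2: 0.75 (25%) and 0.85 (15%).

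With 15 per arm, estimating the slope inflates the ANCOVA variance by 1 + 1/(2×15 - 4) = 27/26 = 1.038:

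| rho | Cut against follow-up ANOVA | Cut against change ANOVA |
|---|---|---|
| 0.5 | 1 - 0.75 × 1.038 = 22% | 1 - 0.75 × 1.038 = 22% |
| 0.7 | 1 - 0.51 × 1.038 = 47% | 1 - 0.85 × 1.038 = 12% |

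Simulation agrees to within about one percentage point.

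**Step 4: which readouts are exposed.** Over 2-24 hours, a response that evolves over weeks should move little. The lymph-node comparison uses a contralateral node sampled at the same moment in the same patient, so time since the course is the same on both sides. That leaves blood at day 7 and day 28.

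**The case against.** The strongest reply is that the plan already does most of what is asked. Section 4.2 makes the ILIT-SCIT comparison the primary objective, section 11.1 disclaims confirming any difference, and the paired test is only optional, with no tissue, readout or time point attached. In an open-label pilot with no single primary endpoint, no confirmatory error rate is at stake. This stands, and it limits the point to attribution in day-7 and day-28 blood.

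A reader might infer four stronger things that the documents do not support:

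- *That drift is present.* No document gives a size or direction. The nearest support is section 3.4, which spaces ILIT injections 4-12 weeks apart so that antigen-specific responses can develop. That suggests evolution over weeks, but it concerns ILIT spacing and not the period after a six-injection SCIT course. At zero drift the paired test errs 5% of the time, as it should.
- *That the plan presents paired tests to day 28 as the effect of ILIT.* Section 11.1 states a goal and does not mention the paired test; section 11.4 does not tie that test to the goal.
- *That the planned ANOVA ignores the pre-injection value.* Section 5.1 frames the blood outcome as immunological changes, so an ANOVA of change is possible. Section 11.4 is silent, and the precision gain is smaller if change was meant and the correlation is high.
- *That the ILIT-SCIT comparison is biased.* Randomisation after the course balances drift in expectation.

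**Conclusion.** The point holds in limited form. With both arms injected after the same course and one pre-injection blood sample, a within-arm blood change at day 7 or day 28 cannot be assigned to the study injection alone. How much this matters depends on drift that the documents do not quantify: across the assumed range of 0 to 0.75 SD, the paired test at n=15 is significant in 5% to 77% of cases with no effect of the injection. The randomised contrast stays at about 5%. It answers how the two regimens differ, not what either does compared with no injection.

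Separately, the plan leaves open whether and how the baseline value enters the arm comparison. Adjusting for it would cut the variance by about 22% at correlation 0.5, and by 12% or 47% at 0.7, depending on the ANOVA intended. Since the primary objective is already comparative and the study descriptive, this is an improvement the team could make. It is not a flaw that undermines the trial.

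**What to change.** In section 11.4:

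1. For each day-7 and day-28 blood readout, estimate the ILIT-SCIT difference adjusted for the patient's pre-injection value, by ANCOVA or a rank-based version where the distribution requires it. Report it with a confidence interval, and base statements about route on it.
2. Report within-arm changes descriptively, with a sentence saying that they may include a continuing response to the preceding SCIT course.
3. Leave the 2-24 hour blood and the lymph-node comparisons as planned.

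The cost is one degree of freedom per model and a few lines of analysis text. No arm, visit, sample or change in clinical management is needed. The fix does not identify the effect of either injection against none; the caveat in item 2 says so to the reader.

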4. STUDY OBJECTIVES

4.1 Overall Objective

The overall purpose of this study is to widely characterize immunological changes induced by ILIT and to evaluate these changes in comparison to SCIT by descriptive statistics. In brief, the study will assess quantity and quality of ILIT- and SCIT-induced immunological changes in lymph nodes and in blood. The two following theories will be investigated addressing the question: Why does SCIT require higher doses and longer than ILIT?

- Quantitative theory: Immunity by SCIT and ILIT is generated by the same cell types and mechanisms, but only a fraction of the SCIT allergen arrives in the regional lymph nodes, hence

weaker effect of SCIT.

- Qualitative theory: ILIT results in a more efficient activation of specialized lymph node cells, different from the vaccination effect activated after SCIT.

The current study is a pilot study including small patient numbers as a basis for bigger follow up studies with a focus on the major ILIT induced immunological changes. The study seeks primarily to determine hallmarks in immunological response (analysis of cell populations and cell culture expression patterns) in lymph nodes and peripheral blood after ILIT versus SCIT.

4.2 Primary Objective

The primary objective is to compare inflammatory responses in blood and lymph nodes from patients receiving grass pollen allergen ILIT or SCIT. No single primary endpoint is defined, as numerous readouts will be performed as part of a wide screening of inflammatory responses.

4.3 Secondary Objectives

As a single secondary endpoint is not defined in this pilot study, primary and secondary endpoints melt together in the overall objective of analysing a wide panel of inflammatory responses to a single ILIT or SCIT.

4.4 Safety Objectives

Although the risk is low when AIT is performed appropriately, allergic reactions do occasionally occur. Part of the inflammatory characterization of ILIT and SCIT will therefore be to assess also local and systemic reaction associated with ILIT and SCIT treatment.

5. STUDY OUTCOMES

5.1 Primary Outcome

The FNA material of lymph node tissue at baseline and 2, 6 or 24 hours after allergen injection (via ILIT or SCIT) will be evaluated for changes in cellular composition and functions.

Immunological changes in peripheral blood at baseline, after 2, 6 or 24 hours, after 7 days and after 28 days of allergen ILIT or SCIT will be analysed by measuring cellular composition and functions in whole blood and in culture blood cells as well as inflammatory proteins and antibodies in serum.

5.2 Secondary Outcomes

To analyse the effect of dose on the measured immunological and inflammatory responses after a single ILIT injection (400 U).

To analyse differences between ILIT and SCIT-induced inflammatory and immunological responses.

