3.3 Preclinical Evidence

ILIT has been successfully performed in various mouse models using purified ovalbumin, bee venom allergen extract or purified phospholipase A1 (Api m 1), recombinant Fel d 1 cat allergen, and birch and grass pollen allergen extracts (19-25). One ILIT study in mice revealed that approximately 100-fold higher allergen doses were found in lymph nodes after ILIT as compared with a subcutaneous injection of the same allergen dose (20). Accordingly, similar therapeutic effects after ILIT with Api m 1 could be reached with only 1% of dose needed after SCIT with the same allergen (20). In another mouse ILIT study, only 0.1% of the SCIT dose was required to obtain comparable results (20, 26).

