8.3 Dose modifications

We already have experiences with dosing Polvac™ from an ongoing study using Polvac™ at our department (BASEC Number: 2021-02301) and with off-label use of up-dosing Polvac™. The ILIT doses used in the trial described in the current protocol is based on the experience from the past trial (133 U) and from off-label treatment of four patients in February to April 2023 (133 U, 200 U and 400 U).

We inject the study dose after patients finished a full cycle of pre-seasonal short-term SCIT scheme with Polvac™ (the patients have therefore reached and tolerated the maximal maintenance dose of 2000 U). The maximal dose in the current study will not exceed the maintenance dose for SCIT (2000 U) and will be much lower for ILIT (400 U) and should therefore be well tolerated by the study participants.

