9.2.2 Assessment of secondary outcomes

Differences in immunological response after injection of ILIT 400 U and SCIT 2000 U via two routes to demonstrate a possible route dependency.

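### An ILIT dose effect is listed with only one ILIT dose, a two-regimen contrast is worded as route dependency, and the Synopsis counts three groups of 10 where the body has two arms of 15

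*Combined protocol and SAP*

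**What the plan says.** **Dose.** The first line of section 5.2 is "To analyse the effect of dose on the measured immunological and inflammatory responses after a single ILIT injection (400 U". Sections 3.5, 6.1, 7.3 and 8.1 and Table 2 give one ILIT dose (0.1 ml, 400 U) and one SCIT dose (0.5 ml, 2000 U). Section 8.3 mentions other ILIT doses, but they come from a separate trial (133 U) and "from off-label treatment of four patients in February to April 2023 (133 U, 200 U and 400 U", not from this study.

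**Route.** Section 9.2.2, on how secondary outcomes are assessed, lists only "Differences in immunological response after injection of ILIT 400 U and SCIT 2000 U via two routes to demonstrate a possible route dependency". The second line of 5.2 asks neutrally for differences between the ILIT and SCIT responses. Section 11.4 says "For comparative testing of the different treatment groups (SCIT versus ILIT), ANOVA is applied" for suitable continuous data, with Kruskal-Wallis otherwise. It contains no dose model or dose contrast.

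**Interpretation.** Section 4.1 sets out two theories. In the quantitative one, "Immunity by SCIT and ILIT is generated by the same cell types and mechanisms", and SCIT is weaker because less allergen reaches the node. The other is "Qualitative theory: ILIT results in a more efficient activation of specialized lymph node cells, different from the vaccination effect activated after SCIT".

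**Numbers.** The Synopsis (study design) randomises to three groups of 10. Its participant-number row gives no calculation and relies on 10 per group to describe three treatments, while its study-product row speaks of two arms. Sections 3.5, 6.1, 7.3 and 8.1 have two arms of 15, section 6.2.1 allocates 1:1, and section 6.2.3 also names two groups. Section 11.2 gives no rationale.

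**The concern.** A listed outcome should correspond to a contrast that the design contains. The dose outcome has none, so the report would owe a result that cannot be produced. This matters because section 3.1 wants the pilot to inform ILIT timing and dosing in later studies.

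The wording of 9.2.2 assigns the between-arm difference to route. Section 11.4 plans between-group tests, so a difference, or the lack of one, could be reported as a finding about route when the injected dose and volume differed as well.

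The only rationale given for patient numbers describes a layout that the body does not have. The 15 per arm in the body therefore has no stated justification.

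**Working it through.** **Inputs.** Table 2: 4000 U/ml undiluted; 0.5 ml SCIT, 0.1 ml ILIT; Phl p 5 900 ng and 180 ng. Sections 7.3 and 8.1: 15 per arm. Section 6.2.1: blocks of six, 1:1. Synopsis: 3 groups, 10 per group.

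**1. The plan's own figures.**
- Doses: 4000 × 0.5 = 2000 U and 4000 × 0.1 = 400 U. Both reproduce.
- Total: 3 × 10 = 30 and 2 × 15 = 30. Both match the stated 30, but 10 and 15 per group do not agree.
- Blocks: 30/6 = 5 blocks, with 3 per arm per block, give 15 per arm. This fits the two-arm layout in the body.

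**2. Dose effect within ILIT.** With 15 ILIT patients all at 400 U, a design matrix with intercept and dose has rank 1 out of 2 columns. No dose effect can be estimated.

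**3. Dose or route effect between arms.** With 30 rows (15 ILIT, 15 SCIT) and columns for intercept, route, dose and volume, the rank is 2 out of 4. The ILIT indicator has correlation −1 with dose, and dose has correlation +1 with volume. There is one contrast for three named factors. The ratios are 2000/400 = 5, 0.5/0.1 = 5 and 900/180 = 5. Reading the dose outcome as 400 U against 2000 U does not help, because dose is then fully aliased with route.

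**4. What a difference in response size could mean.**
- Section 3.8 says: "As compared to a low dose, a high allergen dose is expected to trigger stronger immune responses". A similar or stronger SCIT response could therefore reflect its 5-fold larger dose.
- A stronger ILIT response could not come from a larger injected dose, but it fits both theories. Section 3.3 reports that in mice "approximately 100-fold higher allergen doses were found in lymph nodes after ILIT as compared with a subcutaneous injection of the same allergen dose".
- As an illustration, assume that the mouse ratio carries over to humans and to SCIT given about 1 cm from the node, and that nodal allergen scales linearly with dose. Nodal allergen would then be 100 × (400/2000) = 20-fold higher after ILIT. The arms would differ in opposite directions on injected and nodal dose.
- Response size alone therefore does not separate the two theories.

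**5. Precision under the two layouts.** The 95% half-width for a difference between two groups, in SD units, is t(0.975, 2n−2) × √(2/n).
- n = 10: 2.1009 × 0.4472 = 0.940.
- n = 15: 2.0484 × 0.3651 = 0.748.
- Ratio: 0.748/0.940 = 0.796.

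The layout in the body is the more precise one where every patient contributes. No figure is given for the early time points, because the allocation of patients to 2, 6 or 24 hours is not stated.

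**The case against.** - **The dose line can be read as the effect of 400 U against baseline.** The design can estimate that, with pre-injection blood, contralateral aspirates and paired tests. On that reading, however, the line only repeats the primary outcome in 5.1. What stands is that redefining the line is as acceptable as deleting it.
- **Section 9.2.2 is hedged.** It speaks of a possible dependency and prints both doses, and 11.1 disclaims confirming a difference. The hedge concerns whether a difference exists, not whether route is its cause. What stands is that the fault lies in one phrase and that the second line of 5.2 needs no change.
- **The theories do not rest on response size.** Section 4.1 covers quality as well as quantity, and 9.2.1.4 plans broad cell phenotyping in blood and nodes. This stands in part: the plan already has a better discriminator. But a weaker SCIT effect is part of the quantitative theory, so size does enter the argument.
- **Section 3.8 justifies the study population, and the 20-fold figure needs strong assumptions.** Both are true. The figure is an illustration, and the aliasing in steps 2 and 3 does not depend on it.
- **Section 4.3 merges primary and secondary endpoints.** It does, but the dose outcome is still listed.
- **The n = 10 half-width ignores pooling over three groups.** With 27 degrees of freedom it is 2.052 × 0.447 = 0.918 rather than 0.940. The conclusion is unchanged.

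**Conclusion.** The concern holds on all three parts. The dose outcome cannot be estimated on its literal reading, because there is one ILIT level. The route wording in 9.2.2 is unsupported: one regimen contrast carries route and three 5-fold differences. The Synopsis contradicts the body, and itself, on the number of groups and their size. The first two conclusions follow from the arm definitions alone and need no assumption about effect size or variability.

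The two-regimen pilot design is not at fault. No power figure or error rate is affected, the total stays at 30, and the Synopsis conflict is a contradiction rather than a loss of precision. It should be fixed because the cost is small and the listed outcomes and the rationale for numbers are wrong as they stand. Wording elsewhere, such as the reference in 8.1.1 to a high ILIT dose, is consistent with leftovers from a design with more ILIT groups, but that is an inference.

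**What to change.** 1. **Section 5.2, first line:** delete the dose outcome, or redefine it as something that the two arms can estimate. Leave the second line as it is.
2. **Section 9.2.2:** state the comparison as one regimen against the other (ILIT 0.1 ml, 400 U; SCIT 0.5 ml, 2000 U), and say that route, dose and volume cannot be separated.
3. **Section 4.1:** say that the choice between the quantitative and qualitative theories will not rest on response size alone. Use the cell-type contrast already there, with the caution that it may also depend on dose.
4. **Synopsis:** reconcile the number of groups, the group size and the rationale for numbers with the two arms of 15 in the body. If precision is quoted, 0.75 SD applies at 15 against 15 where all patients contribute. Quote none for the early hours until the allocation to 2, 6 or 24 hours is stated.

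The cost is protocol wording and less ambitious stated aims: no dose result and no claim of a pure route effect. Arms, doses, procedures and the total of 30 are unchanged.
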